8.4.3.7. Physical Examination

Physical examination will consist of full and routine examinations:

Full physical examination will include abdominal, cardiovascular, general appearance, head, eyes, ears/nose/throat, lymph nodes, musculoskeletal, neck, neurological, dermatological, respiratory and other.

Routine physical examinations will include abdominal, cardiovascular, general appearance, respiratory, neurological, and other.

The full examination will be performed at screening and at EOT/ET visit and the routine examination will be performed at baseline, weeks 4, 8, 12, 24 and 36.

If any significant abnormality started prior to informed consent, it will be record in corresponding medical history. If any significant abnormality started after informed consent, it will be record corresponding event on AE form.

8.4.3.8. Body Weight

Body weight will also be measured as safety parameter and recorded in pounds or kilograms.

Criteria for Potentially Clinically Significant Values (PCSV) for Body Weight⁷:

The following criteria for body weight PCSV will be defined:

- Body Weight at post-baseline >=5% increase from baseline
- Body Weight at post-baseline >=5% decrease from baseline

8.4.4. Efficacy Exploratory Endpoints:

8.4.4.1. Nerve conduction test

The Investigator (or sub-investigator) will measure the parameters (CMAP, MUNIX and MUSIX) using the nerve conduction test as described in Table 1 at selected sites. The evaluation results, together with the dates of evaluation, will be recorded in the eCRF. The methods and details will be outlined in the EMG/NCS procedure document.

8.4.4.2. Biomarker Assessment

[REDACTED]

[REDACTED]

[REDACTED]

[REDACTED]

[REDACTED]

[REDACTED]

[REDACTED]

[REDACTED]

8.4.4.3. Additional Biomarker Assessment

At the Sponsor's discretion, potential future testing of exploratory biomarkers related to ALS-disease and edaravone treatment response may include, but is not limited to, markers of

[REDACTED] Whole blood samples will be collected and stored for potential future RNA expression profiling of ALS disease activity and/or edaravone treatment response (RNA testing to be performed at the Sponsor's discretion). The purpose of RNA collection is to develop potential predictive biomarkers through identification of gene expression patterns at baseline that may predict the clinical response (ie, efficacy and/or safety) to edaravone treatment and to develop potential pharmacodynamic markers through characterization of changes in blood cell gene expression included by edaravone.

This additional biomarker data will be summarized and reported in a separate document as needed.

8.5. Analysis Visit Definitions

The acceptable visit dates windows of observation, examination, and investigation are specified as in Table 5. Data obtained within the acceptable windows will be used for analysis or presentation. If the dates of observation, examination, or investigation are out of the following acceptable range, data obtained on those days will not be used for analysis or summary statistics. However, all data as captured will be listed.

The date of the first dose of study drug is defined as Day 1. Unless otherwise specified, baseline will be the last observed value of the parameter of interest prior to the first intake of study drug (this includes unscheduled visits). For other visits, if there are multiple data in a window, the closest data to nominal day will be used. If the distance to the nominal day is the same, the data of later date will be used.

Statistical Analysis Plan
Protocol No. MT-1186-A02

Mitsubishi Tanabe Pharma America, Inc.

Table 5 : The analysis visit windows

Analysis visit	Nominal day	Window	
		Except for laboratory test in Japan site	Laboratory test in Japan site
Baseline	Day 1	\leq Day 1	
Day 8	Day 8	-	Day 2 to 18
Week 4	Day 29	Day 2 to 42	Day 19 to 42
Week 8	Day 57	Day 43 to 71	
Week 12	Day 85	Day 72 to 127	
Week 24	Day 169	Day 128 to 211	
Week 36	Day 253	Day 212 to 294	
Week 48	Day 337	Day 295 to 379	

In case assessments are done at the Early Termination visit, these assessments will be used as data for the scheduled visit closest to the early termination time point, in case the corresponding data are missing from this visit.

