# 17.2 Determination of Sample Size

Assuming the use of a t-test, with a 2-sided alpha level of 5% and a 30% dropout rate up to Week 48, a sample size of 190 subjects per group (380 subjects in total) will provide 85.5% power to detect a treatment effect size of 0.37 (ie, an absolute treatment difference of 2.6 with an associated standard deviation [SD] of 7) in the change from baseline in ALSFRS-R score to Week 48 between oral edaravone 105 mg dose once daily versus oral edaravone 105 mg dose on/off regimen; see details in Appendix 6.

A sample size of 190 subjects per groups will have 78% power to detect statistically significant result if the true hazard ratio (HR) between edaravone 105 mg daily (test) to edaravone 105 mg on/off regimen (control) is HR=0.3. Namely, 70% risk reduction in the hazard assuming 90% survival rate at Week 48 for the control group. This calculation assumes 2-sided alpha of 5% using the log-rank test and a follow-up time of 48 weeks.

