# 17.4.2.2 Handling of Time Point Data in Analyses Performed by Measurement Time Point (Analysis Visit Windows)

For the analyses performed for each measurement time point, the allowable range of data handling for the analysis will be specified as analysis visit window in the SAP.

No data imputation will be performed using data from outside the allowable range. If multiple values are available within the allowable range for the endpoint in question, then the latest value will be analyzed.

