#### 17.4.5 Efficacy Analysis

# 17.4.5.1 Primary Efficacy Analysis

All available ALSFRS-R scores regardless of use of additional/new AMX0035 treatment (ICE1) drug and all available ALSFRS-R scores up to early discontinuation (ICE2) will be included for the primary analysis.

[figure not shown]
The primary efficacy endpoint will be analyzed using a mixed-effect model for repeated measure (MMRM) with terms for baseline ALSFRS-R score, randomization strata of ALSFRS-R rate of decline score during the screening period (2 levels strata of -1,-2 or -3,-4) and geographical region (3 levels strata of Europe, North America, or Asia Pacific), treatment, visit, and treatment-by-visit interaction. The unstructured covariance matrix will be used to model the within-subject errors. Denominator degrees of freedom will be estimated using Kenward-Roger's approximation. The least-squares mean estimates for the mean change from baseline to Week 48, as well as the difference of the estimates between oral edaravone 105 mg daily versus oral edaravone 105 mg on/off regimen will be displayed with their corresponding standard errors, p-values, and 95% CI.

If more than a few death events (≥5% death percentage for all randomized subjects, eg, ≥19 death events) are observed in this study, the primary endpoint analysis using MMRM will be replaced with the ranking score on CAFS score at Week 48 based on a joint rank score derived from change from baseline in ALSFRS-R score and time to death through Week 48 with analysis of covariance (ANCOVA) specified in the secondary endpoint analysis.

If the CAFS analysis is to be used, the following sequence of parametric and semi parametric models will be conducted to estimate the clinical benefit:

- MMRM model as specified above.
- Cox Proportional Hazard Model with terms for treatment as explanatory variable and baseline ALSFRS-R score, randomization strata of ALSFRS-R rate of decline score during the screening period (2 levels strata of -1,-2 or -3,-4) and geographical region (3 levels strata of Europe, North America, or Asia Pacific) as covariates.

[figure not shown]

[figure not shown]

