9.2.1.5. Other Secondary Efficacy Analyses

All available data regardless of use of additional/new AMX0035 treatment (ICE1) drug and all available data up to early discontinuation (ICE2) will be included. For analysis of King's ALS Clinical Stage, if death after early discontinuation (ICE2) was occurred, the death event will be included.

9.2.1.5.1. Changes from baseline in ALSFRS-R score at Weeks 4, 8, 12, 24, 36 and 48

The Change from baseline in ALSFRS-R score at Weeks 4, 8, 12, 24, 36 and 48 will be analyzed using the similar model as specified for the 1st key secondary analysis replacing the %SVC at baseline covariate with ALSFRS-R at baseline. The LSMEANS estimates for the mean change from baseline to Weeks 4, 8, 12, 24 and 36 and 48, as well as the difference of the estimates between oral edaravone 105 mg daily versus oral edaravone 105 mg on/off regimen will be displayed with their corresponding standard errors, p-values, and 95% CI. This endpoint will be analyzed using the FAS. The same analysis will be performed for ALSFRS-R subdomains.

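### SAP 8.5 sets aside a collected early-termination ALSFRS-R or %SVC score that follows a completed visit in the same window, against the protocol's latest-value rule and without declaring the change

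*SAP*

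**What the plan says.** Protocol 17.4.2.2 leaves the visit windows to the SAP but fixes the choice within a window: "If multiple values are available within the allowable range for the endpoint in question, then the latest value will be analyzed".

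SAP 8.5 gives the windows in Table 5 and a different choice: "For other visits, if there are multiple data in a window, the closest data to nominal day will be used". A tie goes to the later date. A separate sentence below Table 5 assigns ET assessments to the "scheduled visit closest to the early termination time point, in case the corresponding data are missing from this visit".

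SAP section 2 says that SAP analysis details override the protocol's, so the SAP rule is the one that would be programmed. SAP section 11 lists two changes from the protocol (physical examination summaries and the FAS definition). This is not one of them.

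Both documents also describe the efficacy data in general terms. Protocol 17.4.5.1 says "all available ALSFRS-R scores up to early discontinuation (ICE2) will be included for the primary analysis", and SAP 9.2.1.5 says "all available data up to early discontinuation (ICE2) will be included".

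Subjects who discontinue have the Week 48 procedures, which include ALSFRS-R and %SVC, within 4 days of discontinuation (SAP 4.1).

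**The concern.** For a discontinuer, the ET score is the last look at function before the data stop. Protocol 9.6 lists worsening of the primary disease, tracheostomy and permanent ventilation among the reasons for withdrawal, so that score often carries the information that explains the dropout.

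The primary CAFS analysis imputes a missing Week 48 ALSFRS-R under MAR (SAP 8.4.2.1 and 9.2.1.1). %SVC, the first key secondary endpoint, uses an MMRM that relies on the same assumption. MAR is more plausible when the model sees the last score. If the score was collected but left out, dropout depends on something the model cannot see, and the estimated Week 48 values tend to be too good.

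The rule is also asymmetric. An ET score before the nominal day, with no scheduled value, is kept and treated as if taken at the later visit, which understates decline. An ET score after a completed visit is dropped, so nothing offsets this.

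Finally, two programmers working from the two documents would build different analysis datasets.

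**Working it through.** **1. Design figures.** Inputs (Protocol 17.2): 190 per group, difference 2.6, SD 7, "with a 2-sided alpha level of 5% and a 30% dropout rate up to Week 48". Evaluable per group: 190 × 0.70 = 133. Noncentrality: 2.6 / (7 × √(2/133)) = 3.03 on 264 df. This gives 85.5% power, as stated. Planned discontinuers: 0.30 × 380 = 114. The documents give no figure for the share whose ET score is set aside.

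**2. One subject under each rule.** Week 24 visit on Day 169, ET on Day 205; both fall in the Day 128–211 window. Protocol: Day 205 is analysed. SAP: Day 169 is analysed (distance 0 against 36). In the mirror case, ET on Day 135 with no Week 24 visit, the score is kept and labelled Week 24, 34 days early. Both rules do this.

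**3. How often the ET score is set aside.** Count the ET days in each Table 5 window that fall after the nominal day, over Days 2–336:

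| Visit | Nominal day | Window | Days after nominal |
|---|---|---|---|
| Week 4 | 29 | 2–42 | 13 |
| Week 8 | 57 | 43–71 | 14 |
| Week 12 | 85 | 72–127 | 42 |
| Week 24 | 169 | 128–211 | 42 |
| Week 36 | 253 | 212–294 | 41 |
| Week 48 | 337 | 295–379 | 0 before Day 337 |

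Total 13 + 14 + 42 + 42 + 41 = 152 of 335 days = 45.4%, assuming uniform dropout, all scheduled visits done on the nominal day and an ET visit for everyone. The score set aside is later than the one kept by a mean of 18.8, median 17 and maximum 42 days.

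Other assumed dropout timings: constant hazard 45.5%, falling 46.5%, linearly rising 44.3%, steeply rising 40.7%.

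**4. All discontinuers.** Multiply 45.4% by the ET completion rate, which the documents do not give: 90% gives 41%, 80% gives 36%, 70% gives 32%, 60% gives 27%. If 19 of the 114 are deaths with no ET visit: 95 × 0.454 = 43 subjects, and 43/114 = 38%.

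**5. The two SAP sentences do not always agree.** Scheduled visit on Day 166, ET on Day 170: the closest-day sentence picks Day 170 (1 day against 3), while the ET sentence keeps Day 166. With visits varied by ±3 days, the share set aside is 42.9% under the closest-day sentence alone and 45.6% under the ET sentence.

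**6. Size of the effect on the Week 48 ALSFRS-R mean (illustrative).** Assumptions, none from the documents: mean slope −11 and SD 5 at Week 48, Brownian deviation SD 4, measurement SD 1 (total √(25 + 16 + 1) ≈ 6.5), 25–32% dropout, log-hazard g per point of excess decline over the previous 28 or 42 days. The Week 48 mean is estimated by maximum likelihood with unstructured covariance, as a stand-in for the MMRM. Ranges over separately coded runs; positive means too favourable:

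| Dropout | SAP rule | Latest-value rule |
|---|---|---|
| g = 0 (unrelated to decline) | 0.12–0.15 | 0.00–0.04 |
| g = 0.5, 28 days | 0.22–0.31 | 0.05–0.12 |
| g = 1, 28 days | 0.36–0.50 | 0.12–0.22 |
| g = 1, 42 days | 0.51–0.57 | 0.22–0.25 |

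**7. Arm difference.** Suppose one arm has g = 1 (28 days) and the other g = 0. Taking the lower ends of the ranges, which come from one run, the SAP rule is off by 0.36 − 0.12 = 0.24 and the latest-value rule by 0.12 − 0.00 = 0.12, so the rule adds 0.12. In a second run it adds (0.45 − 0.15) − (0.19 − 0.04) = 0.15. In the strongest setting it adds at most (0.57 − 0.12) − (0.25 − 0.00) = 0.20. Against 2.6 points these are 5%, 6% and 8%.

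**The case against.** **Precedence is clear.** The SAP says that it overrides the protocol. This stands: there is no doubt which rule would be applied. It does not excuse leaving the change out of section 11.

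**A reader might infer that about half of all discontinuers lose their last score.** The documents do not support that. The 45% assumes an ET visit for everyone, whereas Protocol 10.1.4 foresees subjects who do not return for one, and SAP 3.2.1 reports that the threshold of 19 deaths was crossed. It is an upper bound for all discontinuers.

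**A reader might infer that the closest-day sentence alone always drops the ET score.** It does not (step 5). The ET sentence does that.

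**The clash with the all-available-data wording is weak.** Any rule of one value per window drops a duplicate, and an ET visit up to 4 days after discontinuation may fall outside data up to discontinuation. This stands, and the point does not rest on that wording.

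**Part of the bias has another source.** At g = 0, one run gave +0.01 with scheduled visits only, +0.13 under the SAP rule, +0.02 under the latest-value rule and −0.11 using only post-nominal ET values. So the 0.1 point at g = 0 comes from labelling early ET scores as later visits, not from discarding late ones. The latest-value rule does well there because two timing errors offset each other. This stands. When dropout follows progression, discarding the score adds to the bias.

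**Closest-to-nominal suits visit-specific estimates.** The latest-value rule would label a score from as late as Day 211 as Week 24. That is a real cost, but in the simulations the latest-value rule was also less biased at Weeks 24 and 36.

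**The primary endpoint was not tested.** CAFS ranks deaths on survival time, including deaths after discontinuation, so some of the sickest dropouts need no imputed score. The imputation and sensitivity detail in SAP 9.2.1.1 and 9.2.1.2 is not visible, so separate use of ET data there cannot be excluded. This stands.

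**Conclusion.** The conflict is real and undeclared, and the SAP's version is the less informative one for a MAR analysis. It affects about 41–46% of discontinuers with an ET assessment, given full attendance and the dropout timings tried. That is roughly 27–41% of all discontinuers at 60–90% ET completion.

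The effect on one arm's Week 48 ALSFRS-R mean is modest: about 0.1–0.6 point too favourable, against 0–0.25 under the protocol's rule, on assumptions that are not in the documents. The arm difference moves by about 0.1–0.15 point, at most 0.2, against a design difference of 2.6. It moves only if progression-driven dropout differs between arms; if dropout is alike, the error largely cancels.

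A reader might go further and conclude that the primary CAFS comparison is biased, or that one regimen is favoured. The documents do not support either. No arm imbalance in dropout is given, and the rank analysis with its imputation was not quantified. The point should be corrected before lock because it is cheap to correct, not because it threatens the trial's conclusion.

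**What to change.** In SAP 8.5, for ALSFRS-R and %SVC:

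- When a window holds a scheduled value and a later ET value, use the ET value, as Protocol 17.4.2.2 states.
- Keep closest-to-nominal for other duplicates, such as repeat or unscheduled tests.
- Remove the condition that ET data count only when the scheduled value is missing.
- Feed these values into the CAFS imputation and the MMRMs, and say that the ET assessment counts as data up to discontinuation.

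If the sponsor prefers the current rule, reconcile its two sentences, declare and justify the change in section 11, and add a latest-value sensitivity analysis.

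Cost: about two sentences and one derivation change before lock, with no new data. The downside is small: some interim-visit values will have been taken up to 42 days after the nominal day.

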9. STATISTICAL METHODOLOGY

9.1. Study Subjects

9.1.1. Subject Disposition

Subject disposition will be summarized by treatment group using descriptive statistics. The percentages will be calculated based on the number of randomized subjects, unless otherwise specified.

- The number of subjects screened.
- The number (%) of subjects who failed screening (% calculated from the subjects screened), including the distribution of reasons for screen failure
- The number of subjects randomized to the study (i.e. the number of subjects in the Randomized set)
- The number (%) of subjects in the FAS
- The number (%) of subjects in the SAF
- The number (%) of subjects in the Ex-biomarker Set
- The number (%) of subjects in the Ex-nerve Set
- The number (%) of subjects in the PK Population
- The number (%) of subjects who completed the 48-week double blind period
- The number (%) of subjects who discontinued during the 48-week double blind period including the distribution of reasons for discontinuation
- The number (%) of subjects who continued to the follow up period

9.1.2. Intercurrent Events (ICEs) Distribution

ICEs distribution will be summarized by treatment group using descriptive statistics for the FAS:

- The number (%) of subjects with ICE1 of Additional/new AMX0035 Treatment during the 48-week double-blind treatment
- The number (%) of subjects with ICE2 of Early Discontinuation during the 48-week double-blind treatment period
- The number (%) of subjects with ICE3 of Death Event during the 48-week double-blind treatment period

9.1.3. Protocol Deviations

Protocol Deviation will be listed and the major protocol deviations will be summarized for Randomized. Major protocol deviation will be identified prior to databases lock in the blinded review meeting.

9.1.4. Demographic and Other Baseline Characteristics

Demographics and baseline characteristics will be listed and summarized descriptively by treatment group for all Randomized and FAS. All parameters described in Table 2 will be used for the analysis.

9.1.5. ALS History

ALS History will be listed and summarized descriptively by treatment group for all Randomized and FAS. All parameters described in Table 3 will be used for the analysis.

9.1.6. Medical History

The medical history data will be listed and summarized by treatment group for all Randomized and FAS. Summary table will include frequencies and percentages of subjects with at least one medical history item on the System Organ Class (SOC) and Preferred Term (PT) levels. The table will be sorted by overall descending frequency of SOC and then, within a SOC, by overall descending frequency of PT.

9.1.7. Prior or Concomitant Medications

All prior and concomitant medication will be listed and summarized by treatment group for the FAS. Separate summaries of prior and permitted concomitant medications, (Riluzole and AMX0035), will be presented in tabular form using the ATC Level 4 and PT. Other prior and concomitant medications will be presented in tabular form using the ATC Level 1, ATC Level 2, and PT. Frequencies and percentages of subjects receiving medications will be presented. The tables will be sorted by overall descending frequency of ATC Level(s) and then, within an ATC Level, by overall descending frequency of PT.

9.1.8. Study Medication Exposure and Compliance

Study medication exposure will be calculated as specified in section 8.4.1.5. The following information will be listed and summarized by treatment group for the FAS:

- The number of subjects exposed to study drug treatment
- The number of subjects exposed to study treatment by only oral administration
- The number of subjects exposed to study treatment by PEG/RIG administration
- Duration of exposure (days)
- Total exposure to study drug treatment, expressed as person years (sum of exposure to study treatment)
- Total duration of exposure (days) under PEG/RIG administration
- Time to date subjects switched to PEG/RIG administration (days)

Treatment compliance will be determined by performing study treatment accountability of

Statistical Analysis Plan
Protocol No. MT-1186-A02

Mitsubishi Tanabe Pharma America, Inc.

returned study treatment used and unused according to section 8.4.1.5. Treatment compliance will be summarized and listed for the FAS using descriptive statistics. Non-compliance is defined as taking < 80% or > 120% of study medication during evaluation periods. The proportions of subjects with non-compliance as defined above will be summarized and listed for the FAS.

9.2. Efficacy Analysis

9.2.1. Efficacy Endpoints

For the efficacy endpoints, continuous data will be summarized by treatment group at each analysis visit using summary statistics. Actual values and changes from baseline will be presented. All categorical endpoints will be summarized at each analysis visit, using frequency tabulations.

9.2.1.1. Primary Analysis

More than a few death events ($\geq 5\%$ death percentage for all randomized subjects, eg, ≥ 19 death events) were observed in the data review meeting, the primary endpoint analysis using mixed model repeated measures (MMRM) was replaced with the ranking score on CAFS score at Week 48 based on a joint rank score derived from change from baseline in ALSFRS-R score and time to death through Week 48 with analysis of covariance (ANCOVA) specified in the secondary endpoint analysis. Therefore, the primary analysis will be the CAFS analysis at week 48 using ANCOVA following multiple imputation assuming Missing At Random (MAR) for the FAS.

Statistical Analysis Plan
Protocol No. MT-1186-A02

Mitsubishi Tanabe Pharma America, Inc.

